## **I. Purpose, Background and Rationale**

### **A. Aim and Hypotheses**

**The objective of this study is to explore the safety and feasibility of conducting low-volume, high-intensity interval training (HIIT) on a total body recumbent stepper (TBRS) in persons with stroke in an inpatient rehabilitation setting.** HIIT has emerged as a promising exercise therapy for patients with stroke, with work from the REACH laboratory and others, showing that HIIT leads to improvement in overall walking capacity and endurance.[1-5] Furthermore, in people with stroke, HIIT has been reported to improve aerobic fitness, increase muscle strength, and improve neuroplasticity, which are vital for functional recovery after stroke.[4, 6-9] Previous studies exploring HIIT in stroke have primarily used treadmills, focused on outcomes in functional gait, and included participants with higher walking abilities.[1, 5, 10, 11] Given that many individuals post-stroke, however, experience significant motor deficits, balance impairment, and reduced cardiovascular fitness, HIIT may be more accessible when conducted on a TBRS. The TBRS minimizes upright balance demand, offers adaptations for hemiparesis, and allows for exercise to be prescribed using peak power output, which accounts for motor ability [12]. Previous research conducted by [name] has demonstrated that a single bout of low-volume, short-interval HIIT, performed on a TBRS is safe and feasible in individuals with chronic stroke. Research is required, however, to determine the safety and feasibility of low-volume, short-interval HIIT, performed on a TBRS, in inpatient rehabilitation. Given the nature of increased neuroplasticity during the subacute phase of stroke, compared to the chronic phase[13], implementing an accessible HIIT paradigm during inpatient rehabilitation may prove beneficial for optimizing stroke recovery. **Determining the safety and feasibility of a low-volume, short-interval HIIT program, conducted on the TBRS, is a logical and critical next step in investigating ways to optimize stroke recovery.**

This proposed study will explore the safety and feasibility of HIIT using a recumbent stepper during inpatient stroke rehabilitation. **We hypothesize that a single bout of low-volume, short-interval TBRS HIIT will be safe and feasible in patients with subacute stroke admitted to inpatient rehabilitation.**

We will recruit up to 25 patients admitted to The University of Kansas Acute Inpatient Rehabilitation Unit with subacute stroke, age 18-85 years, to perform a single bout of short-interval (60 seconds), low-volume (10 minutes) HIIT on the TBRS, in line with the protocol used in STUDY00146161 (NCT04673994).

**Aim 1: Explore the safety of short-interval; low volume HIIT in stroke.** Safety will be defined as the presence of no study-related cardiac or serious adverse events.[14] We hypothesize that low-volume, short-

interval, TBRS HIIT will be safe in individuals with subacute stroke while admitted to inpatient rehabilitation during HIIT (**H1a**) and within the 30 minutes following HIIT cessation (**H1b**).

**Aim 2: Explore the feasibility of short-interval, low-volume HIIT in stroke.** Feasibility will be assessed by adherence to the exercise session, attainment of target heart rates, and acceptability of the exercise. At least 75% of participants will complete the entire 10-minute HIIT bout, (**H2a**) and  $\geq 75\%$  of participants will reach target heart rates (75%-85% max HR) during  $\geq 75\%$  of the high-intensity intervals (**H2b**). To examine acceptability, the valid and reliable 8-item Physical Activity Enjoyment Scale (PACES-8) will be used, where higher scores indicate greater exercise enjoyment (**H2c**)[15-19].

### **B. Background and Significance**

Globally, stroke is the second leading cause of death, and third leading cause of death and disability combined, often resulting in significant impairments in physical function and quality of life.[20] Multiple randomized controlled trials have shown that exercise performed before and after stroke decrease the likelihood of having an initial stroke and subsequent strokes, respectively,[21, 22] and exercise-based rehabilitation is crucial for optimizing functional recovery and cardiovascular health post-stroke [4, 6, 10]. However, traditional approaches, such as treadmill training and overground walking at low and moderate intensities, may not effectively stimulate improvements in cardiovascular fitness and may not be inclusive of individuals with a wide range of cognitive and motor abilities post-stroke. Evidence by Billinger et al.,[23] has demonstrated that cardiorespiratory fitness is significantly reduced in individuals with stroke compared to age- and sex-matched peers, and reduced cardiorespiratory fitness is associated with an increased risk for overall mortality[24] and poor functional recovery.[25, 26] This is likely due to the fact that individuals with low cardiorespiratory fitness expend more energy during tasks performed at submaximal effort (i.e., activities of daily living, walking and community activities) when compared to age-matched peers.[27] This results in greater engagement of sedentary behaviors, further exacerbating deconditioning and functional decline. [27, 28] As such, a critical need exists for exercise protocols to be implemented which target cardiorespiratory fitness and recovery post-stroke.

More recently, two randomized controlled trials[5, 29] and a superiority trial [30] sought to compare treadmill-based HIIT to treadmill-based moderate-intensity continuous training[5, 30] or standard of care [29] in participants with late subacute to chronic stroke. Findings indicated that HIIT facilitated the greatest improvements in gait function and cardiorespiratory fitness, and no study-related serious adverse events occurred.[5, 29, 30] Given the promising findings observed with treadmill-based HIIT, implementing more accessible HIIT paradigms for individuals post-stroke may prove beneficial for improving cardiorespiratory fitness and functional recovery.

Recent (NCT04673994) and ongoing (NCT05936008) work from [name] laboratory has been focused on exploring the feasibility of HIIT, using the TBRS, in chronic stroke to provide a more accessible modality for HIIT training. We have previously demonstrated that a single bout of low-volume, short-interval, TBRS HIIT is safe and feasible in individuals with chronic stroke.[14] However, research is required to explore the safety and feasibility of TBRS HIIT in subacute stroke. As neuroplasticity is increased during the subacute phase of stroke recovery, and evidence suggests that HIIT may upregulate neurotrophic factors and corticospinal activity in stroke, [31, 32] HIIT performed during the subacute phase

may further optimize neuroplasticity and recovery while improving cardiorespiratory fitness. This study will provide critical insight into the safety and feasibility of a single session of recumbent stepper HIIT, laying the groundwork for potential future studies seeking to optimize inpatient rehabilitation outcomes for stroke recovery.

**Preliminary Data from [name]:** Exercise post-stroke is complex and requires a well-coordinated, experienced, multi-disciplinary team. Our team has developed the essential infrastructure and processes required to perform rigorous exercise trials in adults with stroke. [name] has built a stroke recovery trial unit, fully integrated with KU Medical Center's physician partners, and has published on the role of physician engagement in successful stroke recovery trials.[33]

[name] has successfully filled and completed enrollment in:

- Two acute stroke studies (n = 38; and n = 15) under 1.5 years as part of her career development award, K01 HD067318 (2011-2016). [name] career development award supported her work in 39 publications.
- An internally funded pilot study in subacute stroke using an 8-week moderate intensity exercise intervention (n = 10) that demonstrated a significant improvement in aerobic fitness with no adverse events.
- Two stroke studies (n = 69; and n = 12) that were conducted on The University of Kansas Inpatient Rehabilitation Unit. [name] has great rapport with the Medical Director of KU's Inpatient unit as well as the chair of the Physical Medicine and Rehabilitation department.
- A trial on the KUMC inpatient rehabilitation unit, which included 20 participants with stroke. Participants were tested after conducting their therapies on the Inpatient Rehabilitation Unit (similar to as proposed in this study).

## II. Research Plan and Design

**A. Study Objectives:** The objective of this study is to explore the safety and feasibility of conducting low-volume, high-intensity interval training (HIIT) on a total body recumbent stepper (TBRS) in persons with stroke in an inpatient rehabilitation setting. The study aims are as follows:

**Aim 1: Explore the safety of short-interval; low volume HIIT in stroke.** Safety will be defined as the presence of no study-related cardiac or serious adverse events.[14] We hypothesize that low-volume, short-interval, TBRS HIIT will be safe in individuals with subacute stroke admitted inpatient rehabilitation during HIIT (**H1a**) and within the 30 minutes following HIIT cessation (**H1b**).

**Aim 2: Explore the feasibility of short-interval, low-volume HIIT in stroke.** Feasibility will be assessed by adherence to the exercise session, attainment of target heart rates, and acceptability of the exercise. At least 75% of participants will complete the entire 10-minute HIIT bout, (**H2a**) and  $\geq 75\%$  of participants will reach target heart rates (75%-85% max HR) during  $\geq 75\%$  of the high-intensity intervals (**H2b**). To examine acceptability, the valid and reliable 8-item Physical Activity Enjoyment Scale (PACES-8) will be used, where higher scores indicate greater exercise enjoyment (**H2c**)[15-19].

**B. Study Type and Design:** We propose a feasibility study with up to 25 participants with subacute stroke (18-85 years of age) admitted to The University of Kansas Acute Inpatient Rehabilitation Unit. Participants will be asked to engage in two visits, both located on the acute inpatient rehabilitation unit.

Visit 1

Visit 1 will take approximately 1 hour to complete. The Total Body Recumbent Stepper (TBRS) Submaximal Exercise Test, which is valid and reliable in persons with stroke, will be used to assess cardiorespiratory fitness. Following completion of the TBRS Submaximal Exercise Test, participants will complete a HIIT familiarization bout. Details on visit 1 procedures can be found in Section E.

Visit 2

Visit 2 will take approximately 1 hour to complete. Participants will complete the single bout of low-volume, short-interval HIIT on the TBRS. Vitals will be monitored throughout the HIIT bout. Details on visit 2 can be found in Section E.

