**C. Sample size, statistical methods, and power calculation**

1. We plan to recruit a sample of up to 25 participants. This sample size aligns with other feasibility trials examining HIIT in stroke.[14, 34]
2. Blinding: No blinding will be used.
3. Analytic and statistical methods to be used: Descriptive statistics will be used to report adverse events, participants who completed the entire HIIT bout, target heart rates achieved, and PACES-8 scores.

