**D. Subject Criteria (See Vulnerable Populations appendix, if applicable):**

We intend to enroll up to 25 participants (18-85 years of age) with subacute stroke admitted to The University of Kansas Acute Inpatient Rehabilitation Unit. Inclusion and exclusion criteria are outlined in the table below.

Inclusion criteria	

-Both sexes between the age of 18-85 years at time of consent

-Ischemic or hemorrhagic stroke at consent. People with stroke and newly diagnosed cardiovascular complications had >50% prevalence of recurrent stroke at 5 years.[35] Index stroke or recurrent stroke on same side as index stroke will be allowed.

-Exercise continuously for minimum of 30 watts for 3 minutes on the recumbent stepper to demonstrate ability to perform the exercise test or therapist confirmation/documentation of participant's ability to use the recumbent stepper.[36]

-No aerobic exercise contraindications[37] or other safety/physical concerns during the submaximal exercise test determined by the therapy team or inpatient physicians.

-Able to communicate with investigators, follow 2-step command & correctly answer consent comprehension questions

---------------------------	---

Exclusion criteria	
 
- Implanted pacemaker or defibrillator limiting exercise performance
 
- Reported pain that limits or interferes with activities of daily living and physical activity/exercise
 
- Acute MI in the last 2 days
 
- Ongoing unstable Angina
 
- Active Endocarditis
 
- Symptomatic Severe Aortic Stenosis
 
- Decompensated HF
 
- Acute PE, PI, or DVT
 
- Acute Myocarditis or Pericarditis
 
- Other significant neurologic, orthopedic, or peripheral vascular conditions that would limit exercise participation
 
- Oxygen-dependent chronic obstructive pulmonary disease
 
- Neurological disease (Multiple Sclerosis, Alzheimer's disease, Parkinson's disease)
 
- Pregnancy
 

---------------------------	---

Withdrawal/Termination of exercise criteria: A participant may withdraw from the study at any time or be withdrawn from the study at the principal investigator's discretion if exercise is deemed unsafe for continuation.

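### Aim 1 calls the bout safe if no qualifying event is seen in up to 25 participants, but zero events in 25 is compatible with a true rate of up to 13.7%

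*Protocol*

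**What the plan says.** Protocol sections I.A and II.A give the same definition under Aim 1: "Safety will be defined as the presence of no study-related cardiac or serious adverse events". The hypothesis in II.A is that "TBRS HIIT will be safe in individuals with subacute stroke admitted inpatient rehabilitation during HIIT" (H1a) "and within the 30 minutes following HIIT cessation" (H1b).

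On size, section II.C says: "We plan to recruit a sample of up to 25 participants". The reason given is precedent: "This sample size aligns with other feasibility trials examining HIIT in stroke". It gives no minimum number, tolerable event rate or precision. The analysis is descriptive: "Descriptive statistics will be used to report adverse events, participants who completed the entire HIIT bout, target heart rates achieved, and PACES-8 scores". Section V.B then expects the single bout to be safe in people with subacute stroke in inpatient rehabilitation.

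The bout that H1a and H1b concern is at visit 2. Section II.E places a submaximal exercise test and a HIIT familiarization, at about the same 70% of peak power, at visit 1. Section II.D allows losses in between: "A participant may withdraw from the study at any time". It also lets the principal investigator withdraw someone for whom continued exercise is judged unsafe.

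**The concern.** The definition turns an observed count of zero directly into the word *safe*, and section V.B applies that word to a population. A count of zero in a small group is weak evidence about a rate, and how weak depends on how many people were exposed. The protocol fixes the verdict but not that number. The same label would follow from zero events in 25 people or in 15, although the second result rules out much less.

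What is at stake is how the result is used afterwards. Section I.B describes the bout as already shown to be safe in chronic stroke, with no rate or limit attached, and uses that as a step towards the present study. It also presents this study as groundwork for later ones. An unqualified label passed on in this way loses its uncertainty.

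**Working it through.** The protocol contains no calculation on this point, so there is no figure of its own to reproduce.

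**Inputs.** Events allowed: 0 (II.A). Maximum n: 25 (II.C). The values n = 20 and n = 15 and the true rates of 2%, 5% and 10% are assumptions for illustration; the protocol gives no minimum, dropout rate or expected event rate. Each participant is taken as independent, with one event/no-event outcome.

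**What zero events rules out.** The exact (Clopper-Pearson) upper limit for 0/n solves (1 − p)^n = α/2 for a two-sided interval, or (1 − p)^n = α for a one-sided bound. With α = 0.05:

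- two-sided: p = 1 − 0.025^(1/n)
- one-sided: p = 1 − 0.05^(1/n)

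For n = 25 these are 1 − 0.025^(1/25) = 1 − 0.8628 = 0.1372 and 1 − 0.05^(1/25) = 1 − 0.8871 = 0.1129.

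| Participants doing the bout | Two-sided 95% upper limit | One-sided 95% upper limit |
|---|---|---|
| 25 | 13.7% | 11.3% |
| 20 (assumed) | 16.8% | 13.9% |
| 15 (assumed) | 21.8% | 18.1% |

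**How often the criterion is met.** The chance of zero events at a true rate p is (1 − p)^n:

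| Assumed true rate | n = 25 | n = 20 | n = 15 |
|---|---|---|---|
| 5% | 0.95^25 = 27.7% | 0.95^20 = 35.8% | 0.95^15 = 46.3% |
| 10% | 0.90^25 = 7.2% | 0.90^20 = 12.2% | 0.90^15 = 20.6% |

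At a given true rate, a smaller study is more likely to meet the criterion, while the limit it can report is wider.

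**The other direction.** The rule is also strict. At an assumed true rate of 2%, a full sample fails it with probability 1 − 0.98^25 = 1 − 0.603 = 39.7%. A zero-event rule is thus a coarse classifier both ways, which is a further reason to report the count with its limit and not only the label.

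**The case against.** The best defence is that this is an exploratory feasibility study with descriptive analysis. The word *safe* appears in a hypothesis and an expectation, not in a fixed conclusion. The counts will be reported, and any reader can compute a limit. Confidence limits and analysis sets are usual content for a statistical analysis plan, which is not at hand. A zero-event rule is easier to meet with fewer people at any sample size, and nothing in the protocol suggests the study will close early.

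Most of this stands, and it limits the point. A reader might infer any of the following, and the documents do not support them:

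- *That 25 is too few, or that a power calculation is required.* The aim is exploration, and no comparison is tested.
- *That the missing interval or denominator is itself an error.* An analysis plan could supply both.
- *That the 75% thresholds of Aim 2 share the fault.* H2a reads "At least 75% of participants will complete the entire 10-minute HIIT bout", which is a benchmark on an observed proportion. The smallest pass at 25, 19/25, has an exact 95% interval of 55% to 91%, but not stating it is again analysis-plan detail.

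What the defence does not remove is the definition. It is fixed in the protocol, it is tied to a sample with a ceiling and no floor, and section V.B carries it to the population. An interval added elsewhere would not change what the protocol says counts as safe.

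**Conclusion.** The point holds as a minor one about wording and reporting. Followed literally, Aim 1 lets a count of zero carry a population statement that it cannot support. At best, with all 25 doing the bout, the data would be compatible with a true rate of up to 13.7% (exact two-sided 95%; 11.3% one-sided). Any loss before visit 2 raises that limit. The choice between the one-sided and two-sided figure does not affect the conclusion.

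The limits rest on independent participants and the binomial model. The figures for 20 and 15 participants and the probabilities of meeting the criterion rest on assumed values. The sample size, the descriptive approach and the zero-event benchmark can all stay.

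**What to change.** Keep the sample size and the zero-event benchmark.

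1. **Sections II.A and V.B** (and the matching text in I.A): state that the number of participants with a qualifying event will be reported with an exact 95% limit, and word the conclusion to match. For example: *no cardiac or serious event related to the study in n participants who started the visit 2 bout (exact two-sided 95% upper limit x%)*, with x recomputed for the actual n. The confidence level belongs in the sentence.
2. **Denominator for H1a and H1b:** those who start the visit 2 bout. Report beside it the number enrolled, any study-related events at visit 1 (exercise test and familiarization), and any withdrawals before visit 2 with reasons. Without these, someone withdrawn after a visit 1 event would vanish from the safety figure, and the result would describe only those who tolerated visit 1.
3. **Section II.C:** add that zero events in 25 gives an exact two-sided 95% upper limit of 13.7%, and that the limit is higher if fewer people do the bout.
4. **H2a and H2b:** leave the denominators as they are. Restricting them to visit 2 starters would change the stated measure and could make the 75% easier to reach. Intervals are optional.

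The cost is a few lines of text and a trivial calculation, with no extra participants or measurements. The downside is that the conclusion reads less favourably: even a study with no events would have to say that rates of up to 13.7%, or more if fewer than 25 take part, are not excluded.

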**C. Sample size, statistical methods, and power calculation**

1. We plan to recruit a sample of up to 25 participants. This sample size aligns with other feasibility trials examining HIIT in stroke.[14, 34]
2. Blinding: No blinding will be used.
3. Analytic and statistical methods to be used: Descriptive statistics will be used to report adverse events, participants who completed the entire HIIT bout, target heart rates achieved, and PACES-8 scores.

**D. Subject Criteria (See Vulnerable Populations appendix, if applicable):**

We intend to enroll up to 25 participants (18-85 years of age) with subacute stroke admitted to The University of Kansas Acute Inpatient Rehabilitation Unit. Inclusion and exclusion criteria are outlined in the table below.

Inclusion criteria	

-Both sexes between the age of 18-85 years at time of consent

-Ischemic or hemorrhagic stroke at consent. People with stroke and newly diagnosed cardiovascular complications had >50% prevalence of recurrent stroke at 5 years.[35] Index stroke or recurrent stroke on same side as index stroke will be allowed.

-Exercise continuously for minimum of 30 watts for 3 minutes on the recumbent stepper to demonstrate ability to perform the exercise test or therapist confirmation/documentation of participant's ability to use the recumbent stepper.[36]

-No aerobic exercise contraindications[37] or other safety/physical concerns during the submaximal exercise test determined by the therapy team or inpatient physicians.

-Able to communicate with investigators, follow 2-step command & correctly answer consent comprehension questions

---------------------------	---

Exclusion criteria	
 
- Implanted pacemaker or defibrillator limiting exercise performance
 
- Reported pain that limits or interferes with activities of daily living and physical activity/exercise
 
- Acute MI in the last 2 days
 
- Ongoing unstable Angina
 
- Active Endocarditis
 
- Symptomatic Severe Aortic Stenosis
 
- Decompensated HF
 
- Acute PE, PI, or DVT
 
- Acute Myocarditis or Pericarditis
 
- Other significant neurologic, orthopedic, or peripheral vascular conditions that would limit exercise participation
 
- Oxygen-dependent chronic obstructive pulmonary disease
 
- Neurological disease (Multiple Sclerosis, Alzheimer's disease, Parkinson's disease)
 
- Pregnancy
 

---------------------------	---

Withdrawal/Termination of exercise criteria: A participant may withdraw from the study at any time or be withdrawn from the study at the principal investigator's discretion if exercise is deemed unsafe for continuation.

#### **E. Specific Methods and Techniques used throughout Study:**

All data collected during the study will be stored on a secure university server database (i.e., REDCap®).

